2 OBJECTIVES, ENDPOINTS, AND HYPOTHESIS

2.1 OBJECTIVES AND ENDPOINTS

Primary Objectives

- To assess the safety and tolerability of a booster dose of Ad26.ZEBOV at a dose of 5×10^{10} viral particles (vp) in children previously vaccinated with the Ad26.ZEBOV, MVA-BN-Filo vaccine regimen with a 56-day interval.
- To assess vaccine-induced humoral immune responses to the Ebola virus glycoprotein (EBOV GP), as measured by FANG ELISA, at 7 and 21 days following a booster dose of Ad26.ZEBOV at a dose of 5×10^{10} vp in children previously vaccinated with the Ad26.ZEBOV, MVA-BN-Filo vaccine regimen with a 56-day interval.

Exploratory Objectives

- To assess neutralising antibody responses directed against the Ad26 vector before booster vaccination as measured by a virus neutralization assay (VNA).

2.2 HYPOTHESIS

As this study is designed to provide descriptive information regarding the safety and immunogenicity of a booster dose of Ad26.ZEBOV in children, no formal statistical hypothesis testing is planned.

3 STUDY DESIGN

3.1 OVERVIEW OF STUDY DESIGN

This is an open label phase 2 study evaluating the immune response to a booster dose of Ad26.ZEBOV administered to children who were previously vaccinated with Ad26.ZEBOV followed by MVA-BN-Filo 56 days later. Only subjects who received the Ad26.ZEBOV and MVA-BN-Filo regimen during their participation in the EBOVAC-Salone trial are eligible for enrolment in this study. Participants will be recruited in two age groups: children aged 4-11 years at the time of dose 1 vaccination and children aged 1-3 years at the time of dose 1 vaccination. Up to 25 subjects will be enrolled in each age group.

The study will consist of a screening period of up to 28 days, a booster vaccination (Day 1) and a post-booster vaccination follow-up period until 28 days post-vaccination (Day 29).

Parents/guardians will be asked to consent for the participation of their children in the study. Children aged 7 years and older at the time of enrolment in this study will be asked to give positive assent for their participation.

After informed consent and assent (if applicable) have been obtained, investigators should ensure that all study eligibility criteria have been met prior to the study vaccination on Day 1 (see list of inclusion and exclusion criteria in Section 4). Eligibility will be based on medical history, physical examinations (including body height and weight), vital sign measurements, a haematological (i.e. full blood count) assessment, and urine pregnancy test in all adolescent girls who are ≥ 12 years of age at the time of screening.

After vaccination, participants will remain under observation at the study site for at least 30 minutes for surveillance for any acute reactions, or longer if deemed necessary by the investigator. Following the vaccination, any unsolicited, solicited local or systemic AEs, and vital signs will be documented by study-site personnel at the end of this observation period.

The participant's parent/guardian will be given a thermometer, ruler and participant diary with instructions for the proper recording of events occurring after the booster vaccination. Diaries will be completed at home by either a project field worker who will visit the participant or by the parent/guardian to document solicited local (at the injection site) and systemic AEs and body temperature, beginning on the evening of the vaccination, and then daily for the next 6 days. Temperatures should be taken at approximately the same time each day, preferably in the evening and additionally whenever the child feels warm. Study-site personnel will collect, review, and complete the participant diary information at the 7-day post-vaccination visit (Day 8).

Unsolicited AEs will be recorded from the booster vaccination (Day 1) onwards until 28 days post-booster vaccination (Day 29). SAEs and/or special reporting situations that are related to study procedures will be reported from the time a signed and dated ICF is obtained onwards until the end of the study (Day 29).

Blood samples will be collected for immunogenicity assessments at Day 1 (i.e. the baseline sample before vaccination), 7 days post-vaccination (Day 8), and 21 days post-dose-vaccination (Day 22). At Day 8 and Day 22, a sample for haematology will also be collected.

Participants will exit the study after 28 days post-vaccination (Day 29). The study is considered completed at the site at final database lock, which will occur after the last participant has completed the last study visit or left the study.

4 PARTICIPANT POPULATION

The study will be open to healthy children (based on physical examination, medical history, a haematological assessment and clinical judgement) who received the Ad26.ZEBOV and MVA-BN-Filo vaccine regimen in the EBOVAC-Salone trial. The children must be enrolled in the long-term follow-up study to the EBOVAC-Salone trial, the VAC52150EBL3005 (EBOVAC-Salone Extension) study but not in the immunogenicity subset.

The inclusion and exclusion criteria for enrolling participants in this study are described in the following two subsections. If there is a question about the inclusion and exclusion criteria, the investigator must consult with the appropriate sponsor representative and resolve any issues before enrolling a participant in the study. Waivers are not allowed.

4.1 INCLUSION CRITERIA

Each potential participant must satisfy all of the following criteria to be enrolled in this current study:

1. Child must be enrolled in the VAC52150EBL3005 (EBOVAC-Salone Extension) study but not in the immunogenicity subset of EBOVAC-Salone Extension study.
2. Child must be a former participant in the VAC52150EBL3001 (EBOVAC-Salone) trial, and have received Ad26.ZEBOV (dose 1) vaccination followed by the MVA-BN-Filo (dose 2) vaccination within the EBOVAC-Salone trial window for dose 2 vaccination.
3. Child must have been aged 1 to 11 years old at the time of dose 1 vaccination in the EBOVAC-Salone trial.
4. The parent/guardian must consent for their child to participate in the VAC52150EBL2011 study by signing (or thumb printing, if illiterate) an ICF, indicating that he or she understands the purpose of, and procedures required for, the study, understands the potential risks and benefits of the study, and is willing to allow their child to participate in the study. If the parent/guardian cannot read or write, the procedures must be explained, and informed consent must be witnessed by a literate third party not involved in the conduct of the study. Children aged 7 years and older will be asked to give positive assent for their participation in the study and the assent procedure must be witnessed by an adult, literate parent/guardian/third party not involved in the conduct of the study, and documented.
5. The parent/guardian is willing/able to ensure that their child adheres to the prohibitions and restrictions specified in this protocol (see Section 4.3)

6. Child must be healthy in the investigator's clinical judgement (and the parent/guardian's judgement) on the basis of medical history, physical examination, vital signs, and a haematological assessment (i.e. full blood count) performed at screening. Subjects must meet the following haematology parameters within 28 days before Day 1:
 - Haemoglobin ≥ 8.0 g/dL for children aged 1 to <5 years, ≥ 9 g/dL for children aged 5 or older
 - Platelet count $\geq 100 \times 10^9$ /L
 - White blood cell count $\geq 5.0 \times 10^9$ /L

Note: The haematological assessment at screening is to be performed within 28 days prior to vaccination on Day 1 and may be repeated if it falls outside this time window.

Note: If haematological screening assessment is out of range and deemed clinically significant, repeating screening test to assess eligibility is permitted once during the screening period, using an unscheduled visit.

7. Adolescent girls who have started their menstrual periods and/or are ≥ 12 years of age at the time of screening, must have a negative urine β -hCG pregnancy test at screening and immediately prior to the booster vaccination on Day 1.
8. The parent/guardian is available and willing to have their child participate for the duration of the study visits.
9. The parent/guardian must have the means to be contacted.
10. The parent/guardian must pass the Test of Understanding (TOU).

Note: If the parent/guardian fails the TOU on the first attempt, he/she must be retrained on the purpose of the study and must take the test again (2 repeats are allowed). If he/she fails on the third attempt, he/she should not continue with enrolling or consenting procedures.

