8.1.3 Vaccination Period

Rationale: Minor editorial changes have been made.

Throughout the document

Rationale: References have been updated.

REFERENCES

SYNOPSIS

TITLE

An open label study to evaluate the safety and immunogenicity of an Ad26.ZEBOV booster dose in children previously vaccinated with the Ad26.ZEBOV and MVA-BN-Filo vaccine regimen.

RATIONALE

Over 600 children have received the adenovirus serotype 26 expressing the Ebola virus Mayinga glycoprotein (Ad26.ZEBOV), modified Vaccinia Ankara Bavarian Nordic vector expressing multiple filovirus proteins (MVA-BN-Filo) Ebola vaccine regimen in the EBL2002 and EBL3001 clinical trials. The vaccine regimen was well-tolerated and highly immunogenic in children; however, the durability of vaccine-induced immune responses is not known. In adults previously vaccinated with the Ad26.ZEBOV and MVA-BN-Filo regimen, a booster vaccination with Ad26.ZEBOV was safe and induced a strong anamnestic response within seven days of the booster vaccination. It is important to establish if a booster dose of Ad26.ZEBOV is safe and immunogenic also in children, as this can guide the clinical use of the Ad26.ZEBOV, MVA-BN-Filo vaccine regimen in this age group. For example, it could support the strategy of boosting immunised children at the start of an Ebola outbreak.

STUDY OBJECTIVES AND HYPOTHESIS

This study aims to evaluate the safety and immunogenicity of an Ad26.ZEBOV booster dose in healthy children who were previously (>2 years) vaccinated with the Ad26.ZEBOV (dose 1) followed by MVA-BN-Filo (dose 2) 56 days later, by monitoring adverse events (AEs) following the booster vaccination and by assessing binding antibody responses using the Filovirus Animal Non-Clinical Group (FANG) Enzyme-Linked Immunosorbent Assay (ELISA).

Primary Objectives

- To assess the safety and tolerability of a booster dose of Ad26.ZEBOV at a dose of 5×10^{10} viral particles (vp) in children previously vaccinated with the Ad26.ZEBOV, MVA-BN-Filo vaccine regimen with a 56-day interval.
- To assess vaccine-induced humoral immune responses to the Ebola virus glycoprotein (EBOV GP), as measured by FANG ELISA, at 7 and 21 days following a booster dose of Ad26.ZEBOV at a dose of 5×10^{10} vp in children previously vaccinated with the Ad26.ZEBOV, MVA-BN-Filo vaccine regimen with a 56-day interval.

Exploratory Objectives

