TIME AND EVENTS SCHEDULE

Study Procedures	Screening (≤28 days) ^a	Study Period				
		Day 1 Booster	Days 2-7	Day 8 (+ 3 days)	Day 22 (± 3 days)	Day 29 ^b (± 3 days)
Test of Understanding (TOU) ^c	X					
Informed consent and assent (if applicable) ^d	X					
Medical history and demographics	X					
Inclusion/exclusion criteria ^e	X	X				
Urine pregnancy test ^f	X	X ^g				
Physical examination ^h	X	X ^f		X	X	X ^b
Vital signs ⁱ	X	X		X	X	X ^b
Vaccine Administration ^d		X				
30 minutes post-vaccination observation ^j		X				
Distribution of participant diary		X				
Completion of the diary at home ^k		X	X			
Completion and review of the diary by study site personnel				X		
Solicited adverse events recording ^j		X	X	X		
Unsolicited adverse events recording		From booster vaccination (Day 1) onwards until 28 days post booster				
Serious Adverse Events ^l		Continuous				
Concomitant medications ^m	X	X	X	X	X	X
Blood draw						
Haematology (i.e. full blood count)	X			X	X	
Immunogenicity (serum) ⁿ		X		X	X	
Approximate blood draw volumes						
Haematology: 2.0 mL per blood draw	2.0			2.0	2.0	
Immunogenicity: Participants aged <6 years, 2.5 mL per blood draw Participant aged 6 years and older, 5.0 mL per blood draw		2.5 5.0		2.5 5.0	2.5 5.0	
Total (Haematology + Immunogenicity)	2.0	2.5		4.5	4.5	
Participants aged <6 years	2.0	5.0		7.0	7.0	
Participant aged 6 years and older						

NOTE: In case of early withdrawal due to an adverse event (AE), the investigator or clinical designee will collect all information relevant to the AE and safety of the participant, and will follow the participant until resolution of the AE or until reaching a clinically stable endpoint. Parents/guardians who withdraw consent, or participants who wish to withdraw assent, will be offered an optional visit for safety follow-up (before the formal withdrawal of consent). Participants and/or parents/guardians have the right to refuse such a visit for themselves/their child.

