^a Screening may be split into multiple days or visits. Retesting of values (eg, safety laboratory) that lead to exclusion is allowed once using an unscheduled visit during the screening period, provided there is an alternative explanation for the out of range value. The safety laboratory assessments at screening are to be performed within 28 days prior of the vaccination (including Day 1 before vaccination) and may be repeated if they fall outside this time window. If retesting is required, all screening procedures (except TOU) should be repeated

^b The Day 29 visit can be conducted via phone call if the participant is unable, or does not wish, to attend the clinic for this visit. If Day 29 visit is conducted over the phone, no physical exam and no vital signs will be collected or recorded for this visit.

^c The TOU should be administered to the parent or guardian who will provide consent, and will be administered after reading but before signing the informed consent form.

^d Informed consent must be obtained before any study-related activities are performed.

^e The investigators should ensure that all study enrollment criteria have been met at the end of the enrolment period and before the booster vaccination on Day 1. If a participant's clinical status changes (including available laboratory results or the receipt of additional medical records) after screening but before Day 1 such that the participant no longer meets all eligibility criteria, then the participant will be excluded from participating in the study.

^f For all adolescent girls who are ≥ 12 years of age at the time of screening.

^g Prior to study vaccine administration.

^h A full physical examination including also body weight and height will be conducted at screening. At following visits, a brief physical examination will be symptom-directed. Physical examination findings (i.e. abnormalities) prior to vaccination are to be recorded as medical history, after vaccination as adverse event(s).

ⁱ Vital signs include blood pressure, pulse/heart rate (at rest), respiratory rate, and body temperature.

^j After the vaccination, participants will remain under observation at the study site for at least 30 minutes for presence of any acute reactions, or longer if deemed necessary by the investigator. Solicited local (at the injection site) and systemic adverse events and unsolicited adverse events emerging during the observation period will be recorded in the CRF.

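### Criterion 7 requires a pregnancy test after menarche or from age 12, but the schedule and section 3.1 test on age alone, so an otherwise eligible menstruating girl under 12 could miss a test that her eligibility requires

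*Protocol*

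**What the plan says.** Three places in the current protocol (version 2.0) say who has a pregnancy test.

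- **Section 4.1, inclusion criterion 7** covers "Adolescent girls who have started their menstrual periods and/or are" aged 12 or older at screening. These girls must have a negative urine "pregnancy test at screening and immediately prior to the booster vaccination on Day 1".
- **Time and Events Schedule, footnote f**, attached to the row "Urine pregnancy test", reads: "For all adolescent girls who are ≥ 12 years of age at the time of screening".
- **Section 3.1**, in its list of the assessments on which eligibility rests, includes a "urine pregnancy test in all adolescent girls who are ≥ 12 years of age at the time of screening".

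Exclusion criterion 6 in section 4.2 removes girls already known to be pregnant or breastfeeding. It does not itself call for a test.

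**The concern.** In criterion 7, the words and/or make menarche a trigger for testing in its own right, separate from age. The other two places drop that trigger. For a girl of 12 or older all three agree. For a girl under 12 who has started her periods, criterion 7 asks for two negative tests, while the schedule and section 3.1 ask for none.

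This matters because sites work from the schedule. Section 8.1.2 says that screening assessments are done as the schedule indicates, and section 8.1.1 presents the schedule as the summary of all study procedures. A team that follows footnote f literally would omit a test on which eligibility depends. At stake is a safety-related entry condition in a paediatric vaccine study, and a deviation that the protocol's own wording would have caused.

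**Working it through.** No statistical figure in the plan bears on this point. The check is a comparison of the texts, followed by a check that the disputed group can occur and how large it might be.

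**1. The three texts applied to each kind of girl**

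| Girl at screening | Criterion 7 | Footnote f | Section 3.1 |
|---|---|---|---|
| 12 or older | test | test | test |
| Under 12, periods started | test | no test stated | no test stated |
| Under 12, periods not started | no test stated | no test stated | no test stated |

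Only the middle row differs. All three texts are current, and the amendment summary does not account for the difference.

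**2. Can the middle row occur?**

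Inputs:
- Age at dose 1, from inclusion criterion 3: "Child must have been aged 1 to 11 years old at the time of dose 1 vaccination in the EBOVAC-Salone trial".
- Time since the primary regimen, from the Synopsis objectives: more than 2 years.

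Age at booster = age at dose 1 + interval. With an interval of just over 2 years, ages at the booster run from about 1 + 2 = 3 years to about 11 + 2 = 13 years. A girl aged 7 to 9 at dose 1 is then about 9 to 11 at screening. The eligible population therefore includes girls just below the age cut-off.

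**3. How many children are in the pool?**

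Inputs:
- Older age group: about 25 children, aged 4 to 11 at dose 1, which is 8 single-year ages (section 10.2 and Synopsis).
- Assumption: ages spread evenly over those 8 years.
- Assumption: half are girls.
- Assumption: 9 years is the lowest booster age of interest.

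For a whole-year interval of 2, 3, 4 or 5 years, booster ages 9 to 11 correspond to dose 1 ages 7–9, 6–8, 5–7 or 4–6. Each is 3 of the 8 single-year ages, so the result is the same for all four intervals. The younger group does not contribute, because its oldest children would be 3 + 5 = 8 at most.

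Girls aged 9 to 11 = (3/8) × 25 × 0.5 = 4.7, or about 5.

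With 40% girls: (3/8) × 25 × 0.4 = 3.8. With 60% girls: (3/8) × 25 × 0.6 = 5.6.

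This is the pool in which the question can arise. The number affected is the part of it that has started menstruating. The documents give no figure for that share.

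**The case against.** The strongest reply is that criterion 7 governs, and that the protocol says so repeatedly.

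- The schedule has an inclusion/exclusion row at both screening and Day 1, and its footnote e tells investigators to confirm all criteria before the booster.
- Section 3.1 itself points to the full list in section 4.
- Section 8.1.2 admits only children who comply with section 4, and the note closing section 4.2 repeats the check before vaccination.
- The opening of section 4 sends questions about the criteria to the sponsor and rules out waivers.
- Medical history is taken at screening, so menarche could be recorded there.
- Neither footnote f nor section 3.1 forbids testing other girls, so a site that applies criterion 7 complies with all three.

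Most of this stands. A reader might infer that the protocol allows a menstruating girl under 12 to be boosted untested. It does not: without the negative tests she fails criterion 7, so she is only otherwise eligible, and vaccinating her would be a deviation. A reader might also take criterion 7 to reach menstruating girls of any age. The criterion sets no lower age for that branch, but it speaks of adolescent girls, a term that the protocol does not define.

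The reply does not remove the conflict. The safeguards work only if staff notice that criterion 7 is wider than the specific testing rule in front of them. Section 3.1 states a narrower rule while describing how eligibility is determined, and the schedule has no separate item for menarche. If criterion 7 governs, the other two texts are incomplete; if they govern, criterion 7 is too wide. Either way the text needs correcting.

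**Conclusion.** The inconsistency is real and the protocol is wrong as written, but the point is small. Following the schedule's testing rule can leave out a test that criterion 7 requires, and the result would be an eligibility deviation.

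A reader might take the figure of about 5 girls as the number who would be exposed. The documents do not support that. It counts all girls aged 9 to 11 under the assumed age spread and sex split. The affected number is an unknown fraction of it and may be zero. Harm of the kind the test guards against would further need an undetected pregnancy within that fraction.

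The sample size, endpoints and descriptive analyses do not depend on this point. That the disputed group can occur follows from the stated ages and interval alone; only its size rests on assumptions.

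**What to change.** Reconcile criterion 7, footnote f and section 3.1 so that all three name the same group of girls. Which definition applies is for the sponsor's clinical team to decide; this review takes no position on it. If menarche stays in the rule, the protocol should also say where it is recorded at screening.

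The cost is one line each in footnote f and section 3.1, or one line in criterion 7, carried in a protocol amendment under section 16.1. If the wider definition is chosen, the extra testing is at most about 2 × 5 = 10 urine tests, even if every girl in the assumed pool needed both.

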4.2 EXCLUSION CRITERIA

Any potential participant who meets any of the following criteria will be excluded from participating in the study:

1. Participants in the EBOVAC-Salone trial who were allocated to the control arm receiving the WHO-prequalified Meningococcal Group A, C, W135 and Y conjugate vaccine.
2. Participants in the EBOVAC-Salone trial who were age 12 years and older at the time of dose 1 vaccination.
3. Known allergy or history of anaphylaxis or other serious adverse reactions to vaccines or vaccine products (including any of the constituents of the study vaccine, e.g., polysorbate 80, ethylenediaminetetraacetic acid or L-histidine for Ad26.ZEBOV vaccine), including known allergy to chicken or egg proteins and aminoglycosides (gentamicin).
4. Presence of acute illness (this does not include minor illnesses such as mild diarrhoea or mild upper respiratory tract infection) or axillary temperature $\geq 38^\circ\text{C}$ on Day 1. Participants with such symptoms will be excluded from enrolment at that time but may be rescheduled for enrolment at a later date within the screening window.
5. Clinically significant history of skin disorder (e.g., psoriasis, contact dermatitis), allergy, symptomatic immunodeficiency, cardiovascular disease, respiratory disease, endocrine disorder, liver disease, renal disease, gastrointestinal disease, neurological illness as judged by the investigator or other delegated individual.
6. Adolescent girls who are known to be pregnant or breastfeeding at screening.

7. Received a blood transfusion or other blood products within 8 weeks of vaccination day.
8. Children who have been vaccinated with live-attenuated vaccines within 30 days before the study vaccination, and with inactivated vaccine within 15 days before the study vaccination.
9. Children who, in the opinion of the investigator, are unlikely to adhere to the requirements of the study or are unlikely to complete the vaccination and observation
10. Any other finding which in the opinion of the investigator or other delegated individual would increase the risk of an adverse outcome from participation in the study, e.g. history of thrombotic thrombocytopenia syndrome (TTS) or heparin-induced thrombocytopenia and thrombosis (HITT).

NOTE: Investigators should ensure that all study eligibility criteria have been met prior to the study vaccination on Day 1. If a subject's clinical status changes (including receipt of additional medical records or available laboratory results) after enrolment but before the vaccination (Day 1) so that he or she no longer meets all eligibility criteria, then the subject should be excluded from participation in the study.

